10.2 Efficacy Evaluation Items

Corneal Thickness

Judgment method: At each visit, based on the corneal thickness examination results described in 7.3.3, a corneal thickness improvement effect is considered present when the thickness reduction in the filled defect area does not exceed 20%.

Evaluation method:

① Effective: The improvement effect is observed at least once before Visit 4 and in a total of two or more visits including the final assessment.

② Ineffective: All cases other than ①.

Corneal Clarity (Degree of Corneal Opacity)

Judgment method: At each visit, based on the slit-lamp examination findings of the cornea described in 7.4.2, corneal clarity is considered good (stromal transparency after repair) when the corneal opacity score is ≤ 2 .

Evaluation method:

- ① Effective: Good corneal clarity is observed at least once before Visit 4 and in a total of two or more visits including the final assessment.
- ② Suggestive effective: Corneal thickness improvement effect is observed at least once before Visit 4, but corneal clarity is judged as poor at the final assessment.
- ③ Ineffective: All cases other than ① and ②.

Visual Acuity and/or Corrected Visual Acuity

Judgment method: At each visit, based on the visual acuity examination results described in 7.3.1, using distance decimal visual acuity, a visual acuity improvement effect is considered present when the visual acuity improves by at least one grade compared with the baseline (preoperative) assessment.

Evaluation method:

- ① Effective: The improvement effect is observed at least once before Visit 4 and in a total of two or more visits including the final assessment.
- ② Ineffective: All cases other than ①.

Judgment when "Insufficient Therapeutic Effect"

Judgment method: When at the final assessment, hydrogel degradation exceeds 20%, corneal opacity score is ≥ 3 , and visual acuity is lower than baseline (preoperative visual acuity), the outcome is defined as "insufficient therapeutic effect."

11. Statistical Matters

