3.2 Study Design

Investigator-initiated, single-center, single-arm, open-label, single-dose trial.

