3.4 Study Method Overview

This clinical study is a single-center, single-arm, open-label, single-dose trial evaluating the safety and efficacy (therapeutic effect) of a sutureless ophthalmic hydrogel for repairing corneal lamellar defects in patients with such defects.

The study consists of a screening period, an implantation period, and an observation period. After obtaining informed consent and completing registration, patients undergo screening examinations to confirm eligibility and absence of exclusion criteria. Surgery is performed under topical anesthesia. Following lesion debridement, the stromal bed is dried with a sponge, and a cotton pad is placed over the pupillary area to protect the fundus. The hydrogel, pre-liquefied in a 37°C water bath, is instilled into the lamellar defect using a sterile syringe, then irradiated with a 365 nm light source at an intensity of 18 mW/cm² for 30 seconds to achieve curing. A bandage contact lens may be applied after the procedure.

On postoperative day 1, gel integrity, thickness, and ocular surface inflammation are assessed using slit-lamp microscopy. During the 8-week observation period following gel injection, subjects are required to attend a total of four follow-up visits (Week 1, Week 2, Week 4, and Week 8). If any safety concerns arise from the trial results, necessary additional measures will be taken, and the specific ethics committee will be notified and must grant re-approval.

The safety of this clinical study will also be evaluated by the ethics committee. After completion of the first subject, the principal investigator may request an ethics

committee meeting based on the occurrence of serious adverse events or other relevant conditions, to seek advice on whether to continue the study or amend the clinical study protocol.

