4.3 Discontinuation Criteria

Subject participation will be discontinued under the following conditions, and after performing the scheduled examinations/observations/evaluations to the extent possible, the reason and course of discontinuation will be recorded in the case report form:

1) When the subject wishes to discontinue participation.

2) When, after obtaining consent, the subject is found not to meet the inclusion criteria or to violate the exclusion criteria.

3) When an adverse event occurs and it is determined that continuation of the study is difficult.

4) When the principal investigator and physician determine that the subject cannot comply with the protocol requirements.

5) When the clinical study itself is terminated.

Additionally, if a serious adverse event occurs, the principal investigator and physician shall report it to the ethics committee for regenerative medicine, etc.

5. Subject Informed Consent Acquisition/Registration

The principal investigator or physician provides oral and written explanation of the study's purpose, methods, etc., of the study to the subject and obtain written consent for study participation.

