8.4.2 Expected harms

8.4.2.1 Hydrogel detachment or displacement

Judgment criteria: Hydrogel displacement or absence in the graft area observed on slit-lamp examination.

Management method: The principal investigator and physicians performing regenerative medicine will discuss the treatment plan during the observation period.

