8.4.2.2 Infection

Judgment criteria: Presence of corneal infiltrate/ulcer, sharp increase of cells in the anterior chamber or hypopyon, ocular discharge, and conjunctival hyperemia.

Management method: The principal investigator and attending physician will immediately discuss the treatment plan. Surgical removal of the hydrogel and aggressive anti-infective therapy will be initiated. Corneal transplantation will be performed if necessary. Corneal smear and culture will be obtained to identify the causative pathogen.

9. Adverse Event Evaluation/Reporting

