11.1 Target Sample Size and Rationale

This clinical study aims to evaluate the use of a sutureless hydrogel for repairing corneal stromal defects. A minimum required sample size of 30 cases is set to confirm the reproducible safety trend of the hydrogel in corneal stromal repair, exploratorily assess its efficacy in repairing such defects, and provide foundational data for future clinical trials.

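### The Section 10.2 responder rules do not ask whether the study hydrogel is still in place, so an eye whose gel was removed or replaced by a corneal transplant can be graded Effective

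*Protocol*

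**What the plan says.** Section 10.2 grades three efficacy items from findings at the visits.

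- **Clarity** is good at a visit when the opacity score is 2 or lower. The eye is Effective when "Good corneal clarity is observed at least once before Visit 4 and in a total of two or more visits including the final assessment".
- **Visual acuity** counts as improved when it is at least one grade above the preoperative value. The same visit pattern gives Effective.
- **Thickness** counts as improved when the filled area has lost no more than 20%. The visit pattern is again the same.

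Ineffective is the residual class for each item. Clarity also has an intermediate grade. A separate label for insufficient effect applies at the final assessment.

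Elsewhere the protocol foresees that the gel may not survive follow-up. For infection, Section 8.4.2.2 provides for surgical removal of the gel and says "Corneal transplantation will be performed if necessary". For detachment or displacement, Section 8.4.2.1 says only that the physicians "will discuss the treatment plan during the observation period". Section 4.3 allows participation to end when an adverse event makes continuation difficult, "after performing the scheduled examinations/observations/evaluations to the extent possible".

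**The concern.** The secondary objective is the therapeutic effect of the hydrogel. The scoring rules look at the state of the cornea on the day and not at what produced it. If infection leads to removal of the gel and a transplant, the surgery is meant to restore what Section 10.2 scores. A failure of the product then stays in the denominator and can enter the numerator as a success.

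The error can only favour the product, and a single-arm study has no comparator to offset it. Section 11.1 intends the results as a basis for later trials, so an overstated rate would be carried into their planning.

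**Working it through.** **Inputs from the protocol**
- Sample size: "A minimum required sample size of 30 cases is set" (Section 11.1). It is not derived from a rate or a precision target, so the plan has no figure of its own to reproduce here. No rate of infection, removal or transplantation is given.
- Visits at Weeks 1, 2, 4 and 8 (Section 3.4). Slit lamp and acuity are done at all four; OCT at Weeks 1, 4 and 8 (Section 6.2.1).
- Residual stromal bed at entry of at least 300 μm (Section 4.1).

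**Assumptions.** The final assessment is the Week 8 visit. All 30 eyes are in the denominator. Total corneal thickness, where needed, is taken as 480 to 600 μm.

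**Step 1: which visit patterns pass.** The rule amounts to good at the final assessment and good at least once earlier.
- Clarity and acuity, four visits: 2^4 = 16 patterns. Eight are good at Week 8 and one of these has no earlier good visit, so 8 − 1 = 7 are Effective.
- Thickness, three OCT visits: 2^3 = 8 patterns, of which 4 − 1 = 3 are Effective.

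**Step 2: place a removal or transplant in those patterns.** Poor, poor, good, good is Effective. With infection in the first weeks and a graft before Week 4, every good visit belongs to the graft. Good, poor, poor, good is also Effective; there the gel was clear once, failed, and the cornea seen at Week 8 is its replacement.

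**Step 3: does another provision make such an eye a failure?**

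| Provision | Why it does not |
|---|---|
| Insufficient effect (10.2) | Needs more than 20% gel degradation, opacity of 3 or more and acuity below baseline, all together. A clear graft fails the opacity condition. |
| Infection and detachment criteria (10.1) | Safety items with no link to the efficacy grade. One eye can be Unsafe and Effective. |
| Discontinuation (4.3) | A matter of judgment, and assigns no efficacy grade. |
| Handling of abnormal data (11.5) | Decided case by case. A valid reading of a clear graft is not plainly missing, unused or abnormal. |

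**Step 4: thickness.** The reference for the 20% limit is not stated.
- If it is gel thickness, complete removal is a 100% loss and fails.
- If it is total thickness of the area, removal down to a 300 μm bed is a loss of (480 − 300)/480 = 37.5% to (600 − 300)/600 = 50%, which also fails. Removal alone passes only if the remaining bed is at least 0.8 × 480 = 384 μm to 0.8 × 600 = 480 μm.
- A graft that restores the thickness of the area can pass on the total-thickness reading.

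**Step 5: size.** One eye moves a rate by 1/30 = 3.3 percentage points. As an illustration, take 24/30 graded Effective: 80.0% (exact 95% CI 61.4 to 92.3). Regrading one eye gives 23/30 = 76.7% (57.7 to 90.1); regrading three gives 21/30 = 70.0% (50.6 to 85.3). The chance that at least one of 30 eyes has such a procedure is 1 − (1 − q)^30. For assumed q of 2%, 5% and 10% this is 45.5%, 78.5% and 95.8%. That is the chance of the event, not of a misgrade, which also needs the visit pattern of Step 1.

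**The case against.** The strongest reply has four parts.

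1. **Discontinuation.** Removal of the only study product followed by a graft may well lead to discontinuation under Section 4.3, and the assessments then done may be a close-out rather than continued efficacy visits. This stands in part. It narrows the gap, but it is discretionary, and the protocol does not define the final assessment.
2. **The failures are visible.** Infection and detachment have their own criteria under the primary, safety objective, and Section 9.4 records the treatment given. This stands. The events are not hidden; Section 10.2 simply does not use them.
3. **Efficacy is exploratory.** It is secondary and descriptive, with no test or threshold. This stands and limits the harm to an overstated descriptive rate.
4. **The analysis plan may deal with it.** One may exist and is not shown. But the protocol itself fixes the grades with a residual class, so a plan that follows it inherits the gap.

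A reader might go further in three ways that the text does not support. One might infer that re-filled eyes are counted as successes. Re-filling is nowhere mentioned, the design is single-dose (Section 3.2), and Section 8.4.2.1 only leaves detachment to discussion. One might infer that every such eye passes all three items. Plain removal would usually fail thickness (Step 4), and an eye with a recent infection or graft may well miss the acuity criterion. And one might put a figure on the total inflation. That would need an event count that the protocol does not give, and every such eye graded Effective.

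**Conclusion.** The point holds in limited form. As written, the clarity and acuity rules can grade an eye Effective after the study gel has been removed or replaced by a transplant, provided that the eye stays in follow-up and meets the visit pattern. The thickness rule shares the fault only if a graft restores the thickness of the area and total thickness is the reference. Each such eye overstates the affected rate by 3.3 percentage points if all 30 eyes are in the denominator; the total is unknown.

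The primary safety result is not affected and no error rate is at stake. This is a should-fix: the effect per eye is modest, but it runs in one direction and is easily prevented before enrolment. Confidence is high on the wording and low on how often it will matter.

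**What to change.** Add to Section 10.2, as a scoring rule that takes precedence over all the grades: an eye in which the study hydrogel is surgically removed, or which receives corneal transplantation or another surgical repair of the treated area before the final assessment, is classed Ineffective for thickness, clarity and visual acuity. Measurements after that date are listed but not used for the grade. Report the number of such eyes beside each rate, and add the procedure date to the case report form.

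Reporting outcomes regardless of later surgery, with the number of operated eyes shown, would be a legitimate supplementary summary. It answers a different question from the effect of the hydrogel and should be labelled so.

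The cost is a short addition to the text and one date field, with possibly slightly lower reported efficacy rates. Clinical management of infection and detachment does not change, and safety follow-up continues as planned.

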6.2 Observation Period: Visits 1~4 (Week 1~Week 8)

6.2.1 Visits 1 (Week 1), Visits 2 (Week 2), 3 (Week 4), 4 (Week 8)

Within each visit window, the following assessments and evaluations will be performed:

- 1) The investigator will inquire about the subject's symptoms and signs since the last visit and the occurrence of any adverse events, with detailed documentation in the electronic medical record.
- 2) Subjects will undergo ophthalmic examinations including: visual acuity (uncorrected and/or corrected), slit-lamp examination (anterior segment photography), intraocular pressure measurement, corneal OCT + panoramic OCT (weeks 1, 4, and 8), B-scan ultrasonography (week 2), confocal microscopy (weeks 4 and 8), corneal topography (weeks 1 and 4), biomechanical assessment (weeks 1 and 4), and fundus photography (week 4).

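### The corneal clarity grades in Protocol 10.2 misorder one pattern: an eye first clear at Week 8 is graded Ineffective, below eyes that are opaque at Week 8

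*Protocol*

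**What the plan says.** Protocol 10.2 (Efficacy Evaluation Items, Corneal Clarity) first sets the per-visit rule: "corneal clarity is considered good (stromal transparency after repair) when the corneal opacity score is ≤ 2" on the 0–4 scale of 7.4.2. It then grades each subject in three tiers.

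- The top tier (tier 1), named *Effective*, applies when "Good corneal clarity is observed at least once before Visit 4 and in a total of two or more visits including the final assessment".
- The middle tier (tier 2), named *Suggestive effective*, applies when "Corneal thickness improvement effect is observed at least once before Visit 4, but corneal clarity is judged as poor at the final assessment".
- The bottom tier (tier 3) reads "Ineffective: All cases other than ① and ②".

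The thickness effect used in tier 2 comes from the thickness item of the same section: "a corneal thickness improvement effect is considered present when the thickness reduction in the filled defect area does not exceed 20" per cent.

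Section 6.2 numbers the visits "Visits 1 (Week 1), Visits 2 (Week 2), 3 (Week 4), 4 (Week 8") and schedules "corneal OCT + panoramic OCT (weeks 1, 4, and 8"). Section 3.5 ends follow-up at 8 weeks. Section 2.2 names corneal thickness and corneal clarity as the main measures for the efficacy objective.

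The end of 10.2 defines a separate outcome, *insufficient therapeutic effect*: at the final assessment, hydrogel degradation above 20%, an opacity score of 3 or more, and visual acuity below baseline.

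**The concern.** Three tiers named *Effective*, *Suggestive effective* and *Ineffective* will be read as an order from best to worst. Tier 2 is open only to eyes that end opaque, because of the condition "but corneal clarity is judged as poor at the final assessment". An eye that ends clear but misses tier 1 therefore has only the bottom tier left.

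Tier 2 is also entered through thickness. No good clarity score is needed at any visit to reach the middle grade of the clarity item.

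At stake is the per-subject clarity grade, on one of the two efficacy measures named in 2.2, in a study that 11.1 says should supply foundational data for later trials.

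**Working it through.** **Inputs.** Clarity is good (1) or poor (0) at Visits 1–4 (Weeks 1, 2, 4, 8), which gives 2^4 = 16 patterns. OCT falls at Weeks 1 and 4 before Visit 4, so the early thickness effect has 2^2 = 4 profiles, 3 of which contain at least one effect. Together that is 16 × 4 = 64 profiles. The final assessment is taken to be Visit 4; the protocol does not define the term. These are logical cases, not expected frequencies.

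**Two readings of tier 1.** Reading A: the final visit must itself be one of the good visits. Reading B: the final visit is only counted in the total.

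- Reading A: final good and at least one of three earlier visits good = 2^3 − 1 = 7 patterns *Effective*.
- Reading B: at least two good of four = 6 + 4 + 1 = 11 patterns *Effective*.
- Difference: 11 − 7 = 4 patterns, namely those good at two or three of Visits 1–3 and opaque at Week 8 (3 + 1).

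**Key patterns under the rule as written**

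| Weeks 1, 2, 4, 8 | Early thickness effect | Reading A | Reading B |
|---|---|---|---|
| 0 0 0 1 | yes or no | Ineffective | Ineffective |
| 0 0 0 0 | yes | Suggestive effective | Suggestive effective |
| 0 0 0 0 | no | Ineffective | Ineffective |
| 1 0 0 0 | yes | Suggestive effective | Suggestive effective |
| 1 1 0 0 | yes | Suggestive effective | meets tiers 1 and 2 |
| 1 0 0 1 | yes or no | Effective | Effective |

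Pattern 0001 fails tier 1 because no visit before Visit 4 is good, and fails tier 2 because final clarity is not poor. It is *Ineffective* in all 4 thickness profiles under both readings.

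**All profiles, Reading A**

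- Clear at Week 8 (8 × 4 = 32): 7 × 4 = 28 *Effective*, 1 × 4 = 4 *Ineffective*. All 4 are pattern 0001.
- Opaque at Week 8 (8 × 4 = 32): 8 × 3 = 24 *Suggestive effective*, 8 × 1 = 8 *Ineffective*.

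**All profiles, Reading B.** Clear at Week 8 is unchanged. Of the 32 opaque at Week 8, 12 are *Suggestive effective* only, 12 meet tiers 1 and 2 together, 4 are *Effective* and 4 *Ineffective*.

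**Clash within 10.2.** Take an eye with a thickness effect at Week 1 that by Week 8 has more than 20% degradation, opacity 3 or more and vision below baseline. It meets *insufficient therapeutic effect* and is also *Suggestive effective* for clarity, above an eye that ends clear.

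**Does replacing the thickness trigger with a clarity trigger suffice?** No. The never-clear eye would drop to *Ineffective*, but the 7 patterns clear earlier and opaque at Week 8 would be *Suggestive effective* under Reading A, still above 0001.

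**The case against.** Asking for a confirmed effect before awarding *Effective* is a legitimate choice, and an eye clear only at Week 8 is unconfirmed. That stands. It justifies keeping such an eye out of tier 1, but not placing it below eyes that end opaque.

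The consequence is limited. Section 11.3 plans frequency summaries at each time point, or cross-tabulation against baseline, for discrete items. Late clearing would therefore show in the Week 8 scores. No test or ordinal score on the tiers is stated, the study is exploratory (3.1), and efficacy is the secondary objective. All of this stands and keeps the point modest.

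Reading A is the more natural one, because tier 2 is contrasted with tier 1 by its poor final result and Reading B makes the tiers overlap. The double reading is therefore a wording matter, and the misordering does not depend on it.

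A reader might infer more than the document supports:

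- That eyes which become clear by Week 8 are generally graded *Ineffective*. They are not: an eye clear at any of Weeks 1, 2 or 4 and again at Week 8 is *Effective*.
- That late clearing is a common course, so that several of the 30 subjects would be misgraded. The protocol gives no time course of opacity and no rates, so any count would be a guess.

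**Conclusion.** The point holds for one pattern. As written, 10.2 places an eye first clear at Week 8 below an eye opaque at Week 8 that had one early thickness effect, even if that second eye was never clear. No other section regrades either eye, and the result is the same under both readings of tier 1.

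The size is 1 of the 8 patterns that end clear. Each subject who follows it is 1/30 = 3.3% of the planned sample; how many will do so cannot be computed from the protocol. The harm is confined to the per-subject clarity grade, since the visit-by-visit scores remain reportable. The one assumption is that the final assessment is Visit 4.

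**What to change.** Reword the clarity tiers in 10.2:

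1. *Effective*: clarity good at the final assessment and at one or more of Visits 1–3.
2. *Suggestive effective*: state explicitly that the thickness trigger is removed. Define the tier as clarity good at the final assessment only, or good at an earlier visit but poor at the final assessment. Report the two sub-groups separately.
3. *Ineffective*: all others, which means eyes never clear.

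The 16 patterns then split 7, 8 and 1, with no overlap, and no eye that ends clear ranks below one that ends opaque. Against Reading A, pattern 0001 moves up (4 of 64 profiles), never-clear eyes with an early thickness effect move down (3), and eyes that lost clarity without a thickness effect move up (7 × 1 = 7).

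As a minor clarification, use the same form (final assessment plus at least one earlier visit) for thickness and visual acuity. Those items have two tiers and cannot show this misordering, but they share the double reading. For visual acuity, measured at four visits, it is again 7 against 11 of 16 patterns. For thickness, with OCT at three numbered visits, it is 2^2 − 1 = 3 against 3 + 1 = 4 of 8.

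The cost is wording only, with no new assessment. The downsides are that an unconfirmed clear result at Week 8 earns the middle tier, and that eyes with maintained thickness but no clarity lose it; their thickness result is still graded under its own item.

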2.2 Secondary Objective

The secondary objective of this clinical study is to evaluate the efficacy (therapeutic effect) of the sutureless ophthalmic hydrogel for repairing corneal lamellar defects, using corneal thickness and corneal clarity as the primary outcome measures.

3. Study Design

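### The middle tier of the corneal clarity grading is triggered by corneal thickness, so an eye that was never clear can be graded Suggestive effective for clarity

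*Protocol*

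**What the plan says.** Protocol section 10.2 takes corneal clarity from the slit-lamp opacity score of section 7.4.2 (0 to 4). At each visit, "corneal clarity is considered good (stromal transparency after repair) when the corneal opacity score is" 2 or less. Three tiers follow:

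- Tier 1 (labelled *Effective*) is the top grade and applies when: "Good corneal clarity is observed at least once before Visit 4 and in a total of two or more visits including the final assessment".
- Tier 2 is worded as follows: "Suggestive effective: Corneal thickness improvement effect is observed at least once before Visit 4, but corneal clarity is judged as poor" when last assessed.
- Tier 3 is the remainder: "Ineffective: All cases other than ① and ②".

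The thickness effect named in tier 2 is defined just above, under a separate item with its own two-level grading: "a corneal thickness improvement effect is considered present when the thickness reduction in the filled defect area does not exceed 20"%. It is measured by anterior segment OCT (section 7.3.3), which section 6.2.1 schedules at Weeks 1, 4 and 8 among the four follow-up visits (Weeks 1, 2, 4 and 8; Visit 4 is Week 8).

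Section 2.2 sets efficacy as the secondary objective, "using corneal thickness and corneal clarity as the primary outcome measures". No section explains why thickness enters the clarity grading.

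**The concern.** Thickness and opacity are different properties, measured by different instruments and graded as separate items. Tier 2 of the clarity item requires no visit with good clarity. It requires only that the gel kept its thickness once and that the eye is opaque at the end. Tier 3 is the remainder, so it inherits the thickness criterion as well.

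A gel that stays in place but leaves the cornea opaque is a failure that a clarity grading ought to show. Under this rule that eye moves up a tier. Some eyes that were clear for a time, which a middle tier would naturally capture, fall to the bottom tier because of thickness. Clarity is one of the two measures named for the efficacy objective, and section 11.1 intends the results as groundwork for later trials.

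**Working it through.** The protocol gives no figure to reproduce. The check applies the rule as written to every possible visit pattern. The counts below are logical patterns, not expected patient frequencies.

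**Inputs.** Clarity is good or poor at Visits 1 to 4 (section 10.2): 2^4 = 16 patterns. The thickness effect is present or absent at the OCT Visits 1, 3 and 4 (section 6.2.1): 2^3 = 8 patterns. Together: 16 × 8 = 128.

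Tier 1 can be read in two ways:

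- *Strict:* good clarity before Visit 4, at the final visit, and so at two or more visits.
- *Loose:* good clarity before Visit 4 and at two or more visits, with the final visit merely among those counted.

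**Never-clear eyes.** Suppose the opacity score is 4 at all four visits and thickness reduction is within 20% at Week 1. Tier 1 fails under both readings. Tier 2 is met, because the thickness effect was seen before Visit 4 and final clarity is poor. The grade is *Suggestive effective*. Of the 8 thickness patterns, only the 2 with no effect at Visits 1 and 3 escape: 8 − 2 = 6 of 8 are upgraded. If thickness were available at all four visits, the count is 16 − 2 = 14 of 16. Both results hold under either reading.

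**Clear earlier, poor at the end.** Seven clarity patterns have at least one good visit before Visit 4 and a poor final visit: 7 × 8 = 56 patterns. The grade is *Ineffective* only where tier 1 fails and no thickness effect was seen at Visits 1 or 3 (2 of the 8 thickness patterns).

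- Strict: all 7 clarity patterns fail tier 1, so 7 × 2 = 14 of 56.
- Loose: only the 3 patterns with a single good visit fail tier 1, so 3 × 2 = 6 of 56.

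**Expected share upgraded.** Let p be the proportion of never-clear eyes with thickness reduction of 20% or less at some visit before Week 8. The share upgraded is p itself. The protocol gives no value, so the range is 0 to 100%. With 30 eyes, each misgraded eye moves a reported proportion by 1/30 = 3.3 percentage points.

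**Rule with tier 2 based on earlier good clarity.**

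| Quantity | As written | Changed tier 2 |
|---|---|---|
| Never-clear patterns graded *Suggestive effective* (either reading) | 6 of 8 | 0 of 8 |
| Clear earlier, poor at end, graded *Ineffective* (strict) | 14 of 56 | 0 of 56 |
| Patterns meeting both tiers 1 and 2 (strict) | 0 of 128 | 0 of 128 |
| Patterns meeting both tiers 1 and 2 (loose) | 4 × 6 = 24 of 128 | 4 × 8 = 32 of 128 |

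The 4 in the last row are the clarity patterns with two or more good visits before Visit 4 and a poor final visit. Under the strict reading, 6 + 14 = 20 of 128 patterns change tier. The last row shows that changing tier 2 alone is not enough: tier 1 must also settle the final-visit requirement.

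**The case against.** The strongest objection is that little depends on these tiers. Safety is the primary objective, clarity is a secondary item, the study is exploratory, and no test or decision rule uses the grades. Section 11.3 provides for summaries of discrete items by time point, so opacity scores can be reported whatever the tier label. The judgement of insufficient therapeutic effect in section 10.2 uses the opacity score directly. All of this stands and limits the severity. It does not make the grade right. The insufficient-effect rule also needs hydrogel degradation above 20% and visual acuity below baseline, so an opaque eye that keeps its gel is not caught by it.

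The mixed tier could also be deliberate. A reader might infer a plain carry-over from the thickness item, because tier 2 repeats tier 1's timing phrase and its contrast with poor final clarity reads naturally only after earlier good clarity. That is plausible, but the protocol does not settle it and the sponsor must say which was meant.

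A reader might further infer that any eye clear at Weeks 1 to 4, opaque at Week 8 and thinned by more than 20% ends as *Ineffective*. The text does not support that in general. Thinning must exceed 20% at every measured visit before Visit 4. An eye clear at several earlier visits is also already *Effective* under the loose reading of tier 1. Nor does the protocol say that tiers 1 and 2 will be pooled into a response rate.

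**Conclusion.** The rule is wrong as written, and severity is moderate. A never-clear eye is graded *Suggestive effective* for clarity whenever the thickness criterion was met once before Visit 4, under either reading of tier 1.

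The reverse error holds under both readings for an eye clear at exactly one visit before Visit 4, poor at the end, and thinned by more than 20% at every measured visit before Visit 4. It extends to eyes clear at several earlier visits only if tier 1 requires good final clarity.

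How many eyes are affected cannot be estimated from the protocol. A reader might take the point as undermining the trial's conclusions, but no error rate, sample size or safety finding depends on it. What is affected is the reported grading of one secondary, descriptive item.

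**What to change.** In section 10.2, let tier 2 apply where the opacity score was 2 or less on one or more visits ahead of Visit 4 and clarity is poor when finally assessed. In tier 1, state explicitly that clarity must also be good at that last assessment. Both changes are needed for the tiers to be exclusive.

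If the sponsor did intend thickness, take that category out of the clarity grading and label it as a combined thickness and clarity category.

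The cost is a sentence in each of two tiers, plus the matching case report form or programming rule. No extra measurement is required. It should be settled before any eye is graded, because a later change could look driven by the results.
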